16.5 Trial Monitoring, Auditing, and Inspecting.....	60
16.6 Quality Assurance and Quality Control.....	60
16.7 Disclosure and Publication Policy	60
17 REFERENCES	62
18 APPENDIX A.....	65
18.1 Quantifying the Level of Disability	66
18.2 EDSS Scoring	66
18.3 Functional Systems.....	66
18.4 Functional System Score	66
18.5 The Scale	69
Response to Non-Hold FDA Issues.....	97

TRIAL SYNOPSIS

Trial title	
Phase I, Open Label Safety Study of Ublituximab for the Treatment of Acute Optic Neuritis and/or Transverse Myelitis in Neuromyelitis Optica (NMO) and Neuromyelitis Optica Spectrum Disorder (NMOSD)

Trial rationale	
Ublituximab (UTX; also known as LFB-R603) is a monoclonal antibody that specifically binds to the trans-membrane antigen CD20. The binding induces an immune response that causes lysis of B cells.
 
The rationale for using ublituximab is based on the known roles of B cells, antibody production and plasma cells in the pathophysiology of NMO. NMO is characterized by the presence of an anti-AQP4 antibody, which is produced by differentiation of B cells to plasma cells. Because these anti-AQP4 antibodies may be pathogenic, B cells recognizing AQP4 may be involved in the disease process as well. B cells also play a role as potent antigen presenting cells in NMO. The strongest evidence of the importance of B cells in NMO comes from studies of B cell depletion, most commonly with anti-CD20 monoclonal antibody, rituximab (Rituxan®).

Product	
Ublituximab, recombinant chimeric monoclonal antibody against CD20 antigen, concentrate for solution for infusion. Ublituximab is manufactured by LFB Biotechnologies (Les Ulis, France) and supplied by TG Therapeutics, Inc.

Phase	Phase I
Trial Sponsor	[name], PhD (Investigator-Initiated Trial-Sponsor)
Trial Chair	[name], PhD John Hopkins University
Trial Objectives	
The overall objective is to assess the safety of ublituximab as add-on therapy to steroids for treatment of acute optic neuritis and/or transverse myelitis in NMO and NMOSD.
 
Primary Objective To assess safety of acute B cell depletion in NMO subjects with acute relapse of optic neuritis and/or transverse myelitis who are treated with ublituximab + steroids beginning on dose administration and ending with repletion of circulating B cells.
 
Secondary Objectives
 
 • To determine the B cell depletion pharmacokinetics of ublituximab in the NMO patient population by monthly B cell counts for up to 9 months. • To determine the frequency of adverse events with ublituximab in this patient population.

	
Clinical secondary efficacy endpoints: Clinical outcomes will be monitored for efficacy using three functional neurologic tests, the Expanded Disability Status Scale (EDSS), Timed 25-Foot Walk and High Contrast Visual Acuity (HCVA). These will be assessed days 1 and 5 of hospitalization, on Days 13 and 20 (if necessary) and at follow up in 90 day and 180 days.
 
Objective secondary efficacy endpoints:
 
 • MRI lesion size • Number of days in hospital • Requirement for plasma exchange rescue therapy 
Pharmacokinetics and Immunogenicity
 
 • To determine the pharmacokinetics of ublituximab in NMO patients • To assess for the effect of immunogenicity on the pharmacokinetics, pharmacodynamics, and safety of ublituximab. 																																																						
Safety Endpoints	All AEs will be reported and evaluated during the treatment period using CTCAE v4.0.																																																						
	
Given the severity and the consequences of relapse in NMO, use of an active treatment is considered mandatory. The potential of currently utilized drugs and techniques to reduce the inflammation in NMO has been established primarily through expert consensus and small open label and retrospective studies.
 
This is a Phase 1 open-label, standard-of-care, single treatment arm, unblinded, single center interventional trial in NMO/NMOSD patients in which experimental subjects will receive one (1) infusion of 450 mg of intravenous ublituximab at the onset of an NMO exacerbation in addition to standard of care treatment with daily intravenous methylprednisolone at a dose of 1000 mg for five days.
 
The trial phases and durations, as well as standard of care treatment and MRIs are shown in the table below. For those who complete the trial, it is comprised of 4 potential phases: Screen, Steroid Treatment, Plasma Exchange (PLEX; if necessary) Treatment and Follow-Up.
																																																						
Trial design	
Table S1: Ublituximab in NMO Trial Phases and Timings of Treatments/MRIs
 
  
 Phase:	Screening 1 day	Steroid Treatment* 5 days	Plasma Exchange (If necessary)	Follow-up Monthly	Follow-up 90-Day Visit	Follow-up 6 Month Visit	
   
 Day	0	1	2	3	4	5	6-20	30, 60, 90, 120, 150, 180, 210, 240, 270	90	180	
 
 	T^{1,2}	T¹	T¹	T¹	T¹					
 
 Treatment Exam/Lab	E/L	E/L	L	L	L	E/L	E/L	L	E	E	
 
 MRI Brain/spine	M					M	M		M*		
  
 
T¹: Administration of methylprednisolone 1000 mg intravenously T²: Administration of 450 mg of ublituximab intravenously E: Neurological examination L: Lab testing M: MRI, as indicated by standard of care; M*: MRI for research purposes
	Phase:	Screening 1 day	Steroid Treatment* 5 days					Plasma Exchange (If necessary)	Follow-up Monthly	Follow-up 90-Day Visit	Follow-up 6 Month Visit	Day	0	1	2	3	4	5	6-20	30, 60, 90, 120, 150, 180, 210, 240, 270	90	180		T ^{1,2}	T ¹	T ¹	T ¹	T ¹					Treatment Exam/Lab	E/L	E/L	L	L	L	E/L	E/L	L	E	E	MRI Brain/spine	M					M	M		M*	
Phase:	Screening 1 day	Steroid Treatment* 5 days					Plasma Exchange (If necessary)	Follow-up Monthly	Follow-up 90-Day Visit	Follow-up 6 Month Visit																																													
Day	0	1	2	3	4	5	6-20	30, 60, 90, 120, 150, 180, 210, 240, 270	90	180																																													
		T ^{1,2}	T ¹	T ¹	T ¹	T ¹																																																	
Treatment Exam/Lab	E/L	E/L	L	L	L	E/L	E/L	L	E	E																																													
MRI Brain/spine	M					M	M		M*																																														

Screening Phase

The purpose of the Screening Phase is to assess subject eligibility. This process includes an MRI scan (standard of care) to identify a contrast enhancing lesion(s) in the optic nerve and/or spinal cord.

Subjects must have a minimum of circulating B cells comprising at least 0.5% of total lymphocyte count to enroll in the trial and receive ublituximab therapy. For those who have not received B cell depleting medications in the past 12 months (rituximab, ofatumumab, ocrelizumab, ublituximab), a normal B cell count of 5-20% of total lymphocytes must be present in the circulation, confirmed by a limited flow cytometry panel of CD3, CD4, CD19 and CD20. For those who have received a B cell depleting medication in the past 12 months, a minimum of 0.5% of total lymphocytes has to be B cells. The working hypothesis is that when a patient has an acute attack following preventive therapy with B cell depleting agents, the remaining or returning B-cells are very aggressive and may catalyze the attack.

Steroid Treatment Phase

High dose (1000 mg) intravenous methylprednisolone will be given to all subjects with MRI-confirmed active lesions at onset of the attack according to standard of care. As early as possible in the Steroid Treatment Phase, 450 mg of intravenous ublituximab will be administered once to each subject enrolled.

Effort will be focused on giving the ublituximab as early in the steroid treatment process as possible. If a subject's admission or transfer to the Johns Hopkins Hospital is delayed, standard of care therapy with steroids will begin as soon as possible at the outside hospital. The subject may then enroll in this trial and receive one dose of ublituximab on the first day of hospitalization at the Johns Hopkins Hospital if the transfer takes place within the Steroid Treatment Phase.

All subjects who fail to clinically respond by day 5 will be recommended for plasma exchange as per standard of care. A beneficial response is generally considered an improvement in the specific deficit(s) that led to the hospitalization. Depending on those specific deficits, the criteria that are routinely used at Johns Hopkins to indicate treatment response(s) in motor, sensory, autonomic and visual function are:

1. An improvement in strength by the Motor Research Council strength scale by at least 1 full point in at least two isolated muscles of at least one limb, or
2. An increase of two Rydel tuning fork units in at least one affected limb.
3. Improvement in bowel and/or bladder function from incontinence to at least partial voluntary control.
4. An improvement in visual acuity using bedside Snellen equivalent of ≥ 2 lines.

If subjects do not require rescue with plasma exchange because they fulfill the clinical criteria above, an MRI may be performed to confirm resolution of the inflammatory lesion to compare to admission MRI. Based on the MRI and other clinical factors, the treating physician may proceed to discharge the subject home or change the plan to escalate immunosuppression to plasma exchange for continued treatment of the acute exacerbation. Before discharge from the hospital, the subject will be scheduled for follow up in the NMO Clinic within 90 days and 6 months. Findings by MRI that may influence escalation to plasma exchange typically include extension of enhancement, involvement of new areas of the nervous system or an increase in the area of T2 hyperintensity. Historically among the NMO/NMOSD

	
subjects treated at Johns Hopkins, approximately 50% of NMO/NMOSD subjects improve from a relapse with steroids alone. The other 50% require escalated care with plasma exchange.
 
Plasma Exchange Treatment Phase
 
Should subjects not meet above clinical criteria to be discharged home, escalation to treatment with plasma exchange is standard of care.
 
The plasma exchange treatment phase begins at the end of the Steroid Treatment Phase and will last up to 14 days. During the Plasma Exchange Treatment Phase, subjects will undergo 1.0 – 1.5 volumes of plasma exchange every other day according to standard of care. At the end of this phase, a second MRI may be performed to compare to admitting MRI. If any further acute immunosuppressive treatment for the acute NMO flare is required and provided according to standard of care, the subject will continue to be followed for safety issues, but the clinical efficacy data will not be included in the statistical analysis. Historically among NMO/NMOSD patients treated at the Johns Hopkins Hospital, approximately 95% of NMO/NMOSD patients who complete plasma exchange are discharged following completion of the plasma exchange.
 
Follow-up
 
Every month after discharge, subjects will be followed with monthly B cell counts until their B cell counts replete to a minimum of 0.5% for patients who will continue to be treated with B-cell depleting agents for preventive care, according to standard of care, or to a minimum of 5% for patients who will use other preventive strategies. In addition, complete blood counts with differential to track neutrophil counts and complete metabolic profiles will be completed monthly as well.
 
The secondary efficacy outcome is neurologic function at follow up 90 days and 6 months after initial hospitalization for the acute relapse. In addition to a thorough history and physical examination, including EDSS rating, visual examination and timed walk, a research MRI of the spine will be performed at day 90 to compare to the relapse lesion.

Trial visits	Screening (Day 0), Steroid Treatment Phase (Days 1 to 5), Plasma Exchange Treatment Phase, if necessary (Days 6 to 20), and Follow-up (monthly blood tests and visits on Days 90 and 180).
Baseline Lab Evaluation (Local Lab)	
 • CBC with differential (3 part differential is acceptable) • Serum chemistry • Serology HIV, HCV, HBV (See Appendix A) • Serum pregnancy test; at screening and at the end of treatment. • Fibrinogen level • B cell count by limited flow cytometry panel
Instrumental tests	
 • MRI of the affected area (brain, cervical spine, thoracic spine) with and without gadolinium contrast.
Dosing Regimen	
All subjects will receive 5 days of intravenous 1000 mg methylprednisolone (referred to generically as “steroids”) as per the current standard of care.
 
Subjects will all receive 450 mg/day of UTX infused over four hours as close to the onset of steroid treatment as possible, during the Steroid Treatment Phase. Therefore all subjects will receive UTX + steroids.
 
All subjects will receive pre-medication prior to infusion of UTX.

	
Premedication: Approximately 30 minutes prior to the infusion of 450 mg/day of UTX, subjects will be pre-medicated with an antihistamine (diphenhydramine 25 mg or equivalent). Use of oral acetaminophen 650 mg (or equivalent) will be allowed for subjects who experience fever or pyrexia, or as clinically warranted.


Inclusion and Exclusion criteria
	
Subjects eligible for enrollment must meet all of the following criteria:
 
 1. Able and willing to provide written informed consent. 2. 18-100 years of age. 3. New acute optic neuritis and/or transverse myelitis. A new clinical event is defined as a clinically significant neurologic deficit(s) on physical exam, not attributable to another disease process, which is different from baseline neurological exam, and attributable to a lesion in the spinal cord, optic nerve or brainstem. New symptoms must be reported within 10 days of onset. 4. Confirmed or highly suspected diagnosis of NMO according to the 2006 revisions of the Wingerchuk diagnostic criteria for NMO (Wingerchuk, 2006), or AQP4 positive NMOSD per the EFNS Guidelines. For NMO, subjects must have two absolute criteria: 
 a. optic neuritis b. myelitis and at least two of three supportive criteria: 
 c. presence of a contiguous spinal cord MRI lesion extending over three or more vertebral segments, d. MRI criteria NOT satisfying the revised McDonald diagnostic criteria for MS [Polman, 2011] e. NMO-IgG (AQP4) in serum. For NMOSD, subjects must have longitudinally extensive transverse myelitis (LETM) recurrent isolated optic neuritis (RION)/bilateral optic neuritis (BON), or opticospinal multiple sclerosis (OSMS) that is NMO-IgG or AQP4 antibody positive. 5. The B cell count must be normal (5-20% of total lymphocytes) in subjects who have not received another B cell depleting therapy in the past year. For those on B cell depleting therapy within the past year, a B cell count of at least 0.5% of total lymphocytes is necessary. 6. A female subject is eligible to enter the trial if she is: 
 ○ Not pregnant or nursing; ○ Of non-childbearing potential (i.e. women who have had a hysterectomy, are post-menopausal, which is defined as >2 years without menses or, in female subjects who have been post-menopausal for <2 years, must be confirmed with Follicle Stimulating Hormone (FSH) and estradiol levels), have both ovaries surgically removed or have current documented tubal ligation) 
OR

Of child-bearing potential (i.e. women with functional ovaries and no documented impairment of oviductal or uterine function that would cause sterility). This category includes women with oligomenorrhoea (even severe), women who are perimenopausal or have just begun to menstruate.

- Subject has a negative serum pregnancy test at screening and agrees to one of the following:
 - a. Complete abstinence from intercourse for the period from consent into the trial until 6 months after the last dose of investigational product; or,
 - b. Consistent and correct use of one of the following acceptable methods of birth control for the period from consent into the trial until 6 months after the last dose of investigational product:
 - i. Oral contraceptives (either combined or progesterone only)
 - ii. Injectable progesterone
 - iii. Levonorgestrel implants
 - iv. Estrogenic vaginal ring
 - v. Percutaneous contraceptive patches
 - vi. Intrauterine device (IUD) or intrauterine system (IUS) with a documented failure rate of <1% per year
 - vii. Male partner sterilization (vasectomy with documentation of azoospermia) prior to the female subject's entry into the trial; this male must be the sole partner for the subject
 - viii. Double barrier method: condom and an occlusive cap (diaphragm or cervical/vault caps) with a vaginal spermicidal agent (foam/gel/film/cream/suppository).

Exclusion Criteria

Subjects meeting any of the following criteria are **not** eligible and cannot enroll in the trial:

1. Current evidence or known history of clinically significant infection including:
 - a. Chronic or ongoing active infectious disease requiring long term systemic treatment such as, but not limited to: progressive multifocal leukoencephalopathy (PML), chronic renal infection, chronic chest infection with bronchiectasis, tuberculosis, or active hepatitis C.
 - b. Previous serious opportunistic or atypical infections.
 - c. History of positive serology for hepatitis B.
 - d. Prior history, or suspicion, of tuberculosis (TB).
 - e. History of positive serology for HIV.
2. History of clinically significant CNS trauma (e.g. traumatic brain injury, cerebral contusion, spinal cord compression)
3. Past or current history of medically significant adverse effects (including allergic reactions) from:

	
 a. Corticosteroids b. Diphenhydramine c. Murine or mouse/human chimeric antibodies 
4. Past or current malignancy, except for
 
 a. Cervical carcinoma Stage 1B or less b. Non-invasive basal cell and squamous cell skin carcinoma c. Cancer diagnoses with a duration of complete response (remission) >5 years 
A history of hematologic malignancy excludes a subject from participation, regardless of response.
 
5. Significant concurrent, uncontrolled medical condition including, but not limited to, cardiac, renal, hepatic, hematological, gastrointestinal, endocrine, immunodeficiency syndrome, pulmonary, cerebral, psychiatric, or neurological disease which could affect the subject's safety, impair the subject's reliable participation in the trial, impair the evaluation of endpoints, or necessitate the use of medication not allowed by the protocol, as determined by the PI of the trial.
 
6. Use of an investigational drug or other experimental therapy for a condition other than NMO within 4 weeks, 5 pharmacokinetic half lives or duration of biological effect (whichever is longer) prior to screening.
 
7. Current participation in any other interventional clinical trial. Participation in non-interventional trial requires approval of the protocol by investigator.
 
8. Subjects who are concurrently receiving any other investigational agents, or have participated in an interventional clinical trial within the last 21 days, or subjects who have been vaccinated with a live vaccine < 2 months prior to trial inclusion.
 
9. Because there is an unknown but potential risk for adverse events in nursing infants secondary to treatment of the mother with ublituximab breastfeeding should be discontinued if the mother is enrolled.

Number of subjects	Five (5) subjects will be enrolled to receive UTX + steroids.
Populations	
Intention-To-Treat (ITT) – all subjects who received one dose of trial medication (UTX)
 
Per Protocol (PP) – all subjects who performed all visits in accordance with protocol without significant protocol deviations or violations
 
Safety Population – all subjects that receive one dose of trial drug (UTX)

Statistical issues	
Primary Safety Assessments: A summary of the number and percentage of subjects with any adverse event (AE), any serious adverse event (SAE), adverse events leading to permanent discontinuation of trial drug and trial drug-related adverse events will be reported.
 
Secondary Efficacy Assessments: Change in neurologic outcomes on the EDSS, Timed 25-Foot Walk and HCVA scales from admission to discharge (Day 5 or 21), and follow up (Days 90 and 180) will be analyzed by paired t-tests with significant p-values considered less than 0.05. A clinical neurologic improvement is commonly

	observed in > 66% of NMO subjects treated at the Johns Hopkins Hospital. The degree of improvement in this trial population has not been adequately quantified historically. By MRI, length of T2 hyper-intensity and length of T1-post contrast enhancement should be stable or reduced by discharge. A paired t-test will be used to compare these values with significance considered at p-values less than 0.05.
Sample size	The sample size of 5 subjects in this single arm study (UTX + steroid) is based on feasibility and logistical considerations on the number of subjects that will ensure a reliable safety report of ublituximab-mediated B cells depletion in the NMO patient population. An independent Data and Safety Monitoring Board (DSMB) will be composed of five members with at least one member who is an Infectious Disease Specialist, Hematologist, Neurologist, Statistician, and another independent expert with experience on assessing safety. Three of the DSMB members will be on staff at the Johns Hopkins University. The DSMB will be reviewing the safety data after the first two subjects are enrolled and completing the Steroid Treatment Phase to determine if it safe to continue the trial. The DSMB will submit their findings to the Sponsor after every meeting and to the IRB. DSMB meetings can be in-person or via teleconference or a combination of the both. The data to be used for review by the DSMB will be actual raw data recorded in the database. The clinical data will be monitored by TG Therapeutics and will be query-free prior to review by the DSMB.
Duration of Subject Participation	Up to 9 months

Abbreviations and Definition of Terms	
Ab	Antibody
ADCC	Antibody-Dependent Cellular Cytotoxicity
AE	Adverse Event
ALP	Alkaline Phosphatase
ALT	Alanine aminotransferase
AQP4	Aquaporin-4
AST	Aspartate aminotransferase
ATC	Anatomic Therapeutic Class
BON	Bilateral Optic Neuritis
Ca	Calcium
CBC	Complete Blood cell Count
CDC	Complement-Dependent Cytotoxicity
CLL	Chronic Lymphocytic Leukemia
CRF	Case Report Form
CNS	Central Nervous System
CRO	Contract Research Organization
CTCAE	Common Terminology Criteria for Adverse Events
CV	Curriculum Vitae
D, d	Day
DSMB	Data and Safety Monitoring Board
EC	Ethics Committee
ECG	Electrocardiogram
EDDS	Expanded Disability Status Scale
Fab	Fragment antigen binding (region)
Fc	Fragment crystallizable (region)
FU	Follow-up
GCP	Good Clinical Practice
HCVA	High Contrast Visual Acuity
IEC/IRB	Independent Ethics Committee (IEC) or Institutional Review Board (IRB)
Ig	Immunoglobulin
ICH	International Conference on Harmonisation of Technical Requirements for Registration of Pharmaceuticals for Human Use
IMP	Investigational Medicinal Product
IRB	Institutional Review Board
IV	Intravenous
kD	kilo Dalton
LDH	Lactate Dehydrogenase
LFTM	Longitudinally Extensive Transverse Myelitis
LLT	Lowest Level Term
MRT	Mean Residence Time
mAb	Monoclonal Antibody
MedDRA	Medical Dictionary for Regulatory Activities
MRI	Magnetic Resonance Imaging
MS	Multiple Sclerosis
NCI-WG	National Cancer Institute – Working Group
NMO	Neuromyelitis Optica
NMOSD	Neuromyelitis Optica Spectrum Disorder
OSMS	Opticospinal sclerosis

Abbreviations and Definition of Terms

PD	Pharmacodynamic or Progressive Disease
PML	Progressive Multifocal Leukoencephalopathy
PPS	Per Protocol Set
PT	Preferred Term
PN	Preferred Name
RCT	Randomized Clinical Trial
RION	Recurrent Isolated Optic Neuritis
SAE	Serious Adverse Event
SAP	Statistical Analysis Plan
SmPC	Summary of Product Characteristics
SOC	System Organ Class
SPE	Serum Protein Electrophoresis
t _{1/2}	Half-Life of Elimination
V	Visit
WHO	World Health Organization

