Twenty-three infusion-related reactions (IRRs) were reported in 20 patients, 16 of them grade 2 and 7 (3 in part I, 4 in part II), grade 3. Sixteen of these 23 IRRs occurred after the first infusion of ublituximab, 3 after the second infusion and 4 after subsequent infusions. Grade 3 infusion-related reactions required infusion interruption and resolved without sequelae after symptomatic treatment such as corticosteroid, antihistamines, oxygen therapy, and bronchodilators in case of bronchospasm.

Twenty three episodes of drug-related pyrexia were reported in 20 patients; mild (< 39°C) for 20 episodes and moderate (from 39 to 40°C) for 3 episodes. Headaches, chills, nausea and asthenia were all reported as mild to moderate AEs.

Fifteen drug-related infections were reported in 9 patients. Ten of these AE's were mild to moderate respiratory tract infections, herpes recurrences or anal abscesses. One grade 3 listeriosis was diagnosed at the time of the 4th infusion followed by a grade 3 bronchopulmonary aspergillosis 2 months later. One grade 3 varicella was reported in one patient and required IV treatment with acyclovir. Another patient with a medical history of aortic valve replacement and staphylococcal endocarditis receiving ublituximab presented with 2 grade 4 episodes, *Streptococcus agalactiae* sepsis then *Staphylococcus aureus* sepsis with endocarditis. Evolution was favorable after antibiotic therapy. All these infections resolved without sequelae except *Staphylococcus aureus* sepsis complicated with endocarditis, which resolved after valve replacement.

Twenty episodes of drug-related neutropenia were observed in 15 patients as well as 2 additional cases of febrile neutropenia. Eight episodes (40%; 4 in part I and 4 in part II) were grade 3 neutropenia and 7 episodes (35%; 3 in part I and 4 in part II) were grade 4. In part I, all episodes but one occurred within 8 days after the first dose and resolved spontaneously despite continuation of the treatment with ublituximab. By contrast, in part II, grade 3-4 neutropenia was observed after the third infusion in 3 cases, after the 7th or 8th infusion in 3 cases, and later in the last two cases. Treatment with granulocyte colony stimulating factor (G-CSF) was started in 4 cases leading to recovery to normal value within 1 to 3 days. Four cases resolved spontaneously.

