7 TRIAL ASSESSMENTS AND TREATMENT

Given the severity and the consequences of a relapse in NMO, use of an active treatment is considered mandatory. The potential of currently utilized drugs and techniques to reduce the inflammation in NMO has been established primarily through expert consensus and small open label and retrospective studies.

This is Phase 1, unblinded safety trial in NMO/NMOSD subjects in which subjects will receive one (1) infusion of 450 mg of intravenous ublituximab at the onset of an NMO exacerbation in addition to standard of care treatment with daily intravenous methylprednisolone at 1000 mg for five days.

The trial phases and durations, as well as standard of care treatment and MRIs are shown in the table below. For those who complete the trial, it is comprised of 4 potential phases: Screen, Steroid Treatment, Plasma Exchange (if necessary) Treatment and Follow-Up.

Table S1: Ublituximab in NMO Trial Phases and Timings of Treatments/MRIs

Phase:	Screening 1 day	Steroid Treatment* 5 days					Plasma Exchange (if necessary)	Follow-up Monthly	Follow-up 90-Day Visit	Follow-up 6 Month Visit
Day	0	1	2	3	4	5	6-20	30, 60, 90, 120, 150, 180, 210, 240, 270	90	180
Treatment		T ^{1,2}	T ¹	T ¹	T ¹	T ¹				
Exam/Lab	E/L	E/L	L	L	L	E/L	E/L	L	E	E
MRI of affected area	M					M	M		M*	

T1: Administration of methylprednisolone 1000 mg intravenously
T2: Administration of 450 mg of ublituximab intravenously
E: Neurological examination
L: Lab testing
M: MRI, as indicated by standard of care; M*: MRI for research purposes

Screening Phase

The purpose of the Screening Phase is to assess subject eligibility. This process includes an MRI scan (standard of care) to identify a contrast enhancing lesion(s) in the optic nerve and/or spinal cord.

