9 TRIAL CALENDAR/EVALUTION TABLE

Table 6: Schedule of Events

Phase:	Screen (1 day)	Steroid Treatment (5 days)					Plasma Exchange (if necessary)	Follow up		
		1	2	3	4	5		Monthly	90 day	6 month
Day	0	1	2	3	4	5	6-20	30, 60, 90, 120, 150, 180, 210, 240, 270	90	180
MRI of the affected area (brain, c/t spine)	M					M	M		M	
Administration of treatment		Steroids on days 1-5 UTX: 1 dose on day 1 or as early as possible in this phase								
Informed Consent	X									
Eligibility	X									
Demographic, NMO and Medical History	X								X	X
Prior NMO treatments	X									
Vital signs, weight	X	X	X	X	X	X			X	X
Neurological Exam	X	X	X	X	X	X			X	X
Laboratory assessment	X	X	X	X	X			X		X
HCVA		X			X	X			X	X
EDSS		X			X	X			X	X
Timed 25-Foot Walk		X			X	X			X	X
Adverse Events		X	X	X	X	X			X	X
Concomitant Meds	X	X	X	X	X	X				

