12.10 IMMUNOGENICITY AND PHARMACOKINETICS

12.10.1 Pharmacokinetic (PK) Sampling:

Patients will have pharmacokinetic (PK) sampling (serum) performed as noted on the schedule below:

Time point
Pre-dose
1 min prior to EOI
30 min post EOI ¹
6 hour post EOI ²

24 hour post EOI ³
72 hour post EOI ³
168 hour post EOI ³

EOI: End of Infusion

¹ +/- 5 minutes

² +/- 30 minutes

³ +/- 2 hours

PK Sampling Procedures - IMPORTANT

Stop and start times of UTX infusion must be recorded and actual time/dates of samples drawn must be provided. The subject will not receive any additional infusions of ublituximab.

All samples to be obtained for PK analysis of ublituximab will be serum. One 6-ml blood sample is required for each sample time point.

After centrifugation, 2 aliquots of 0.5 ml of serum should be stored at -20°C to 70°C at the site. One aliquot will be sent to TG Therapeutics and the second aliquot will be shipped to TG Therapeutics after the first sample is received by them. All samples must be sent within 14 days of being collected from the subject.

Approximately seven (7) samples over 7 days should be collected for the PK analysis of ublituximab.

12.10.2 PK Sample Collection and Processing:

- a. Peripheral blood is to be drawn into heparinized vacutainer tubes. The patient's initials, time sample obtained, and date sample was obtained should be recorded on each tube as well as on the respective PK timesheet in the CRF.
- b. Within 20 minutes of collection, centrifuge the blood samples at 900xg for 15 minutes to separate plasma.
- c. For each sample collected, pipette duplicate aliquots of plasma, 2 ml each, in polypropylene cryovials (Nunc). Aliquot 1 is the sample and aliquot 2 is the duplicate.
- d. Aliquots are to be frozen and stored at -20°C to -70°C or lower until specimens are shipped to TG Therapeutics. All samples must be shipped within 14 days following collection for further storage and/or analysis.
- e. Specimens can be batched for shipment once all samples have been collected for a patient within 14 days of being collected.

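### A subject discharged after the steroid phase without plasma exchange has no scheduled blood count between Day 5 and Day 30, which leaves part of the early neutropenia window in the protocol's own data unmeasured

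*Combined protocol and SAP*

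**What the plan says.** Table S1 (synopsis and Section 7) marks laboratory tests on Days 0 to 5, again in the Days 6-20 column, and then on Days "30, 60, 90, 120, 150, 180, 210, 240, 270". The Days 6-20 column applies only to subjects who need exchange. The synopsis list of visits reads the same way: "Plasma Exchange Treatment Phase, if necessary (Days 6 to 20), and Follow-up (monthly blood tests and visits on Days 90 and 180".

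A subject who meets the response criteria by Day 5 can leave hospital at that point, since "the treating physician may proceed to discharge the subject home". After discharge, the synopsis states that "complete blood counts with differential to track neutrophil counts and complete metabolic profiles will be completed monthly as well". Section 5.4 also requires blood counts and a metabolic profile in follow-up but gives no frequency.

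Section 13 names four events for the DSMB to follow: neutropenia, thrombocytopenia, infection and raised liver enzymes. Section 12.6.2 makes every grade 3 or 4 laboratory abnormality an adverse event and assigns each subject a maximum grade per test.

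**The concern.** Safety is the primary outcome, and three of the four events named for the DSMB are laboratory findings. An abnormality that causes no symptoms enters the data only if blood is taken while it is present. The schedule is dense for five days and then, without exchange, empty until Day 30. The protocol's own first-in-human data place early neutropenia partly inside that empty interval.

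Two things are at stake. The maximum grade per test could be recorded too low for such a subject. The DSMB could also decide on enrolling the next three subjects without any later count from an unexchanged subject.

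**Working it through.** No planned figure needs reproducing: the sample size of 5 rests on feasibility. The check lays the laboratory days over the reported risk window.

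**Inputs**
- Laboratory days without exchange (Table S1): 0, 1, 2, 3, 4, 5, 30, 60 and so on.
- Risk window (Section 1.2, Safety): "In part I, all episodes but one occurred within 8 days after the first dose".
- Dose day *d*: Day 1 as planned, or later in the steroid course after a transfer (Sections 5.3 and 7). I take steroid Day 5 as the latest and count trial days from the start of steroids.
- Share not needing exchange (synopsis, historical): "approximately 50% of NMO/NMOSD subjects improve from a relapse with steroids alone".

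**Length of the gap.** 30 − 5 = 25 days. If monthly testing is counted from a Day 5 discharge, the next count falls near Day 5 + 30 = 35, a gap of about 30 days.

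**Part of the window without a count.** The window ends on Day *d* + 8, and the last count is on Day 5.

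| Dose day *d* | Window ends | Days without a count |
|---|---|---|
| 1 | 9 | 6-9 |
| 2 | 10 | 6-10 |
| 3 | 11 | 6-11 |
| 4 | 12 | 6-12 |
| 5 | 13 | 6-13 |

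**Other blood draws.** Section 12.10.1 includes a sample at "168 hour post EOI", on Day *d* + 7: Day 8 for a Day 1 dose, Day 12 for a Day 5 dose. It is a drug-level sample with no count ordered. The Section 12.10.4 samples at 2, 30 and 60 days are for antibodies. Neither closes the gap.

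**Subjects affected.** At the historical 50%, 5 × 0.5 = 2.5 subjects are expected on this path. The chance of at least one is 1 − 0.5⁵ = 0.969. Among the first two subjects it is 1 − 0.5² = 0.75.

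**DSMB timing.** Section 4.1 triggers the first review after two completed infusions or six months. Section 13 says after two subjects complete ublituximab and steroids, or six months. The synopsis says after two complete the steroid phase. Each of these can be met by Day 5 of the second subject, 25 days before that subject's next scheduled count if there is no exchange.

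**The CLL counts.** Section 1.2 is internally consistent: of 20 episodes, 8 (40%) were grade 3 and 7 (35%) grade 4. Part I had 4 + 3 = 7 of grade 3-4 and part II had 4 + 4 = 8. The part II timings also sum to 8: three after the third infusion, three after the seventh or eighth, two later. No onset day within the 8-day window and no duration is given for part I.

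**The case against.** The strongest reply is that the plan already covers the first part of the window. For a Day 1 dose, Table S1 marks tests on each of Days 1-5, and an episode is lost only if it begins after Day 5 and resolves before Day 30. Adverse events of any kind are recorded for 30 days after treatment (Sections 12.6.1 and 12.6.3), so symptomatic cytopenia or infection would still be captured. The 8-day timing comes from CLL patients on weekly infusions. In part II, which used 450 mg doses, grade 3-4 neutropenia came only after three or more infusions. Monthly counts are stated consistently, so this is a design judgement and not a contradiction.

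All of that stands, and it narrows the point without removing it. This trial gives a single infusion, so the timing after a first dose is the closer precedent, though an imperfect one.

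Three stronger readings are tempting but unsupported:
- A reader might take the 45% neutropenia figure in Section 1.2 as the rate at risk of being missed. It pools all grades, both parts, and courses of 4 or 8 weekly infusions, so it is not an early or single-dose rate.
- A reader might infer a biased contrast, with exchanged subjects showing more events because they are tested more. No such comparison is planned in this single-arm trial of five with summary statistics.
- A reader might see a conflict between Table S1 and the "Laboratory assessment" row of Table 6. The marks in that table, including those for the efficacy tests, may have shifted when the file was read, so nothing is built on it here.

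**Conclusion.** The gap is real: without plasma exchange, Table S1 and the synopsis schedule no blood count for 25 days after Day 5, and no other section available orders one. It overlaps the part I neutropenia window on about Days 6-9 for a Day 1 dose, and on up to Days 6-13 for a dose given late in the steroid course. Symptom-free, self-resolving cytopenia or liver enzyme elevation in that interval could be missed in the primary safety tabulation, and the first DSMB review could come before any later count.

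The size of the under-count cannot be derived. The documents give no onset days or durations for part I episodes, no split of all 20 episodes by part, and, in the text available, no timing for thrombocytopenia or liver enzymes. It would go too far to say that a Day 30 count would miss early neutropenia; it could.

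The conclusion assumes that the unspecified laboratory entries on Days 1-5 include a blood count, which favours the plan. It also assumes that the historical 50% roughly holds under ublituximab. The text following the neutropenia summary in Section 1.2 was not available and could add to the timing data.

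**What to change.** Reconcile the laboratory schedule in Table S1, the synopsis Follow-up text and Section 5.4 with the timing data in Section 1.2 and the DSMB event list in Section 13. State in one place which tests each laboratory entry contains and what applies to a subject who is not exchanged.

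For endpoint measurement only, run the CBC with differential and liver panel already used in the trial on the existing 168-hour PK draw in every subject. Include the results in the safety tabulation and in the data sent to the DSMB. This sets no dose, rescue or stopping rule.

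The cost is one extra tube per subject at a draw already required, plus the table and text edits. One added time point narrows the gap but does not close it.
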